- Each desaturation sequence step will last approximately 2 to 6 minutes. All three Desaturation Sequences are presented in Figure 3 below:
 - Sequence #1: steps # 1-8
 - Sequence #2: steps # 9-13
 - Sequence #3: steps # 14-18 [REDACTED]
- The first two desaturation sequences are conducted in subject specific normocapnia and the third desaturation sequence will be conducted under [REDACTED].
 - [REDACTED]
 - [REDACTED]
 - [REDACTED]
 - [REDACTED]
- Modifications to the hypoxia sequence for patient safety will be left to the judgment of the Principal Investigator.

This document is electronically controlled. Printed copies are considered uncontrolled.

Confidential MDT16010MAVJB3	[REDACTED]	[REDACTED]	[REDACTED]
---------------------------------------	------------	------------	------------

- Study Blood Draws:

[figure not shown]
- At each plateau, after ~ █ minutes wait time (stability period) and extended wait time ~ █ minutes for return to room air and 100% oxygen saturation steps, two paired (simultaneously drawn) jugular bulb vein and arterial blood samples are drawn (█). Draw waste or leader blood samples prior to the draw of paired blood samples may be used to ensure the accuracy of blood samples.
- Co-oximetry is used to determine the jugular venous saturation ($SjvO_2$) and arterial saturation (SaO_2). Each blood sample will be analyzed multiple times or using multiple co-oximeter machines. Blood samples will be averaged to provide one $SjvO_2$ and one SaO_2 value for each paired draw at that plateau. Blood samples are analyzed in real-time and results from the co-oximeters will be stored electronically.
- Co-oximetry raw data (co-oximeter blood oximetry results and the time of analysis) will be provided to Medtronic. █
█
█
█
- The jugular sample will be drawn approximately over a period of █ (targeting rate of █).
○ The arterial sample will be drawn at approximately the midpoint of the jugular bulb draw.
○ Each blood draw (either venous or arterial) is approximately 1.5 ml, totaling approximately █ ml per paired sample (pair = 1 jugular plus 1 arterial).
○ With a target of two paired samples per plateau step, a total of █ paired arterial and venous draws may be collected during the study. Total blood draw during the study is estimated to be █. If less than the targeted █ pairs of blood samples are collected, it will not be considered a protocol deviation.

After the procedure:

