## 5. Investigation Plan

This is a prospective data collection, non-randomized, single center study to validate an investigational Next Generation INVOS system. An investigational next generation INVOS Near Infrared Spectroscopy (NIRS) system includes production equivalent [REDACTED] System (investigational preamplifiers, monitor, and associated cables) in conjunction with Adult sensor [REDACTED] (INVOS system).

This study will be conducted in three phases: Enrollment Phase, Desaturation Phase, and Follow-up Phase. During enrollment phase, subjects will be screened and qualified subjects will be enrolled. After enrollment, during desaturation phase, two investigational INVOS sensors are placed on the patient's forehead and other sensors may be placed on somatic sites. The Next Generation INVOS system will be evaluated for a targeted range of 70-100% arterial blood oxygen saturation (SpO2) levels that are measured by a pulse oximeter. Hypoxic mixtures of gas are delivered and INVOS and SpO2 data are collected at approximately 5-minute intervals during periods of ascending and descending concentration of control of blood carbon dioxide and oxygen levels. At each plateau, blood samples are drawn simultaneously from both jugular bulb and the radial arterial catheters and analyzed for hemoglobin oxygen saturation levels using a co-oximeter.

- 2 sensors on cerebral site (left, right side of forehead)
- 2 blood draws and monitor measurements at each oxygenation plateau
- 1st data point at beginning of each sequence for trending accuracy used for baseline reference
- Somatic Trending Accuracy data is collected for all Sequences #1-3. [REDACTED] does not have an effect on somatic blood oxygenation levels.

This document is electronically controlled. Printed copies are considered uncontrolled.

Confidential MDT16010MAVJB3	[REDACTED]	[REDACTED]
---------------------------------------	------------	------------

During the invasive breathe-down protocol, a subject breathes varying levels of oxygen (desaturation sequence) while paired venous and arterial blood draws are collected. [REDACTED]

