## **7.8. Evaluation of Objectives**

The next generation [REDACTED] system measures hemoglobin under the Sensor, allowing determining absolute levels of blood oxygenation saturation in the tissue (StO2). The INVOS algorithm determines the StO2 values for the tissue under the sensor. The next generation INVOS system will be validated over a clinical range of arterial oxygen saturations (e.g. pulse oximeter) of 70 - 100% in healthy volunteers. Next generation INVOS regional saturation (rSO2) performance will be compared to the calculated global field saturation (fSO2) value obtained from simultaneous arterial and jugular venous blood samples for the cerebral site and it will be compared to legacy INVOS rSO2 on the somatic site. Human volunteers will undergo oxygen desaturation in order to test the system over a clinical range of arterial oxygen saturation levels of 70 - 100%.

The cerebral tissue saturation can be estimated using the saturation of arterial blood (SaO2) and jugular bulb venous saturation (SjvO2).

This document is electronically controlled. Printed copies are considered uncontrolled.

Confidential MDT16010MAVJB3	[REDACTED]	[REDACTED]
---------------------------------------	------------	------------

Co-oximetry is used to determine the  $SjvO_2$  and  $SaO_2$  values ( $SaO_2$  value is taken as the average of the 2 arterial blood samples). The arteriovenous ( $fsO_2$ ) saturation is calculated as a 75:25 ratio of venous to arterial blood.

$$fsO_2 = (0.75 \times SjvO_2) + (0.25 \times SaO_2).$$

Global field saturation,  $fsO_2$  is calculated as approximation of the cerebral oxygen saturation and is used as the reference value for assessing accuracy for cerebral.

[figure not shown]
Overall accuracy will be evaluated:

At the cerebral site, by comparing next generation INVOS  $rSO_2$  with blood  $fSO_2$  values.

[figure not shown]

Trending accuracy will be evaluated:

At the cerebral site, by comparing the next generation INVOS  $rSO_2$  with blood  $fSO_2$  values.

[figure not shown]

At the somatic site, by comparing next generation INVOS  $rSO_2$  with legacy INVOS  $rSO_2$  values.

This document is electronically controlled. Printed copies are considered uncontrolled.

Confidential MDT16010MAVJB3		
---------------------------------------	--	---

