Arithmetic Root Mean Square (ARMS), standard deviation of the error and mean bias will be calculated as defined in the equations below. The primary endpoint will be evaluated to calculate pooled subject ARMS. The equations below represent calculations for overall accuracy with the error component of each equation being replaced with the error as defined in Figure 2 for trending accuracy.

$$Arms = \sqrt{\sum_{i=1}^n \frac{((rSO_2)_i - (fSO_2)_i)^2}{n}}$$

$$Std\ Dev = \sqrt{\sum_{i=1}^n \frac{((rSO_2)_i - (fSO_2)_i - Bias)^2}{n - 1}}$$

$$Bias = \sum_{i=1}^n \frac{((rSO_2)_i - (fSO_2)_i)}{n}$$

This document is electronically controlled. Printed copies are considered uncontrolled.

Confidential MDT16010MAVJB3		
---------------------------------------	--	--

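### Does the trending A_RMS count each sequence's baseline reading as a zero error and so flatter two of the three primary components?

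*SAP*

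**What the plan says.** The primary objective (SAP section 4) has three components: cerebral accuracy, cerebral trending accuracy and somatic trending.

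SAP section 7.8 writes out A_RMS, SD and bias for overall accuracy, each with a sum over i = 1 to n. For trending it keeps the equations, "with the error component of each equation being replaced with the error as defined in Figure 2 for trending accuracy". Under the line "Trending accuracy will be evaluated", the section names the comparator for each site (blood fSO2 for cerebral, the legacy INVOS for somatic). The accompanying figures are missing from the text available here.

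SAP section 5 gives the sampling scheme: "2 blood draws and monitor measurements at each oxygenation plateau", with the first "data point at beginning of each sequence for trending accuracy used for baseline reference". It adds: "Somatic Trending Accuracy data is collected for all Sequences #1-3".

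Protocol section 10.5.1 sets the sequence lengths: "Sequence #1: steps # 1-8", "Sequence #2: steps # 9-13" and "Sequence #3: steps # 14-18".

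SAP section 6 sets minimum pair counts separately by endpoint and capnic state in Table 2, whose contents are blacked out.

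**The concern.** Trending is naturally read as change from the first reading of the sequence. On that reading the baseline's own error is a value minus itself, so it is zero by construction. The sentence in section 7.8 mentions only a new error term and is silent on n. Taken literally, the sum and the divisor carry over unchanged from overall accuracy, and each sequence then adds nothing to the numerator and one full count to the denominator.

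The effect would run in one direction: retained zeros can only lower A_RMS. Two of the three primary components are trending, so a device slightly over its limit could be reported as meeting it. Forced (0,0) points in the trending regression, Bland-Altman and concordance analyses would be a further consequence. A related worry is that a baseline resting on one of the two draws at the first plateau passes its noise to every later error in the sequence.

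**Working it through.** **The plan's own figure.** The only readable size is 25 subjects per endpoint (SAP section 6). It cannot be reproduced, because the assumed A_RMS, its SD, the power and alpha are blacked out. No trending n is readable.

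**Size of the effect, if it existed.** Suppose k of N pooled errors are zero by construction and all N are counted. Then

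A_RMS(retained) / A_RMS(excluded) = sqrt((N − k) / N).

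Inputs: 8, 5 and 5 steps (Protocol section 10.5.1); 2 draws per plateau (SAP section 5); one zero per sequence (the assumption under test). The target pairs are 8 × 2 = 16, 5 × 2 = 10 and 5 × 2 = 10, or 36 in all.

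| Sequences pooled | N | k | Ratio | Understatement |
|---|---|---|---|---|
| 1 | 16 | 1 | sqrt(15/16) = 0.968 | 3.2% |
| 2 or 3 alone | 10 | 1 | sqrt(9/10) = 0.949 | 5.1% |
| 1 and 2 | 26 | 2 | sqrt(24/26) = 0.961 | 3.9% |
| 1, 2 and 3 | 36 | 3 | sqrt(33/36) = 0.957 | 4.3% |

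For all three pooled, the largest true value that would still read as passing is 1/0.957 = 1.044 times the criterion, or 4.4% over it. The number of sensors multiplies N and k alike and cancels.

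**Dependence on the assumed construction.** Other readings of the same visible text give other answers:

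- Baseline readings not scored: k = 0, understatement 0%.
- One baseline for the whole session: 1 − sqrt(35/36) = 1.4%, or 1 − sqrt(25/26) = 1.9% for Sequences 1 and 2.
- Both first-plateau draws zero: 1 − sqrt(14/16) = 6.5% for Sequence 1, 1 − sqrt(8/10) = 10.6% for a five-step sequence, 1 − sqrt(22/26) = 8.0% for Sequences 1 and 2, and 1 − sqrt(30/36) = 8.7% for all three.

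So the arithmetic behind 3–5% is right, but it follows from one assumed construction.

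**Does the text establish that construction?**

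1. The trending error is defined by reference to Figure 2. In these formulas n is simply the number of errors entering the sum. If Figure 2 defines the error for post-baseline readings only, n counts only those, and the sentence in section 7.8 is correct as it stands.
2. SAP section 5 assigns the first reading the role of reference. No readable sentence also makes it an evaluated point.
3. SAP section 6 sets pair minimums by endpoint, which is compatible with a smaller count for trending than for overall accuracy.
4. The regression, Bland-Altman and concordance items in section 7.8 are described on rSO2 against fSO2 or the legacy rSO2. No readable text says they use change scores, so the forced (0,0) points are not established either.

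**The single-draw baseline.** With independent unit-variance draw errors, a later point's trending error has variance 1 + 1 = 2 with a one-draw baseline and 1 + 0.5 = 1.5 with a two-draw mean. The ratio sqrt(1.5/2) = 0.866 is a 13% reduction. If half the variance is shared within a plateau, the two-draw figure is 1 + 0.5 + 0.25 = 1.75, and sqrt(1.75/2) = 0.935 is about 6%. Both correlations are assumed. Section 7.8 already takes SaO2 as the mean of the two arterial samples, and the description of the pairing at the end of section 5 is partly blacked out, so how many draws stand behind the baseline cannot be read. At the somatic site the comparator is a device, so blood-draw noise does not enter that reference.

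**The case for a change.** The strongest contrary argument combines two passages. Section 7.8 states one change to the formulas, the error term, and no change to the range of the sum. SAP section 7.1.3 makes inclusion of all available data for enrolled subjects the default unless something else is specified. Together they could be read as keeping the baseline pair until some text removes it, and no readable text does. Table 2 does not settle the matter, since it is described as a minimum to be collected and not as a list of pairs to be scored.

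Part of this stands. The readable text does not state that the baseline pair is dropped, and Table 2 does not prove exclusion. But section 7.1.3 defines which subjects and data enter the analysis; it does not turn a reference value into an observation of its own error. Dropping a reading that serves only as reference discards no outcome data. The silence on the index range also cannot be held against the plan when the definition it points to, Figure 2, cannot be read here. What is left is a point of detail that a look at the figure would settle.

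**Conclusion.** No understatement is shown. The 3.2% to 5.1% range by sequence (4.3% for all three pooled) is correct only if exactly one zero-error reading per sequence is counted, every target pair is obtained, and nothing in Figure 2 restricts the points scored. If baseline readings serve only as reference, as SAP section 5 describes them, the effect is 0%.

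The consequence for passing or failing could not be sized in any case, because the A_RMS criterion and the expected A_RMS are blacked out. Averaging both first-plateau draws would redefine the trending endpoint on assumed error correlations. That is a design preference and does not correct an error.

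The conclusion rests on Figure 2 and Table 2 being unreadable here, which is not a defect of the plan. It would change only if Figure 2 explicitly scored the baseline reading.

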**Cerebral Accuracy Overall and Trending:**

- 1 Regression of the [REDACTED] rSO2 data vs. the reference fsO2 data with the calculation of  $r^2$  assessing the strength of the linear relationship between the two continuous variables. Calculations and fitted line plots will be performed for pooled population data. Regression coefficients, slope and intercept will be reported with bootstrap 95% Confidence Limits.
- 2 Bland Altman plot (Bland and Altman, 1986), (Bland and Altman, 2007) defined limits of agreement provide the approach to agreement between different methods for measuring the same quantity. Individual subject and pooled population data will be graphed.
- 3 Random Coefficients Model; subject dependent variable added to model as random effect. Regression coefficients, slope and intercept will be reported with bootstrap 95% Confidence Limits.
- 4 Concordance correlation coefficient (CCC) analysis (Lin, 1989). This index is the correlation between the two paired measurements that fall on the 45° line through the origin.

**Somatic Accuracy Trending:**

- 1 Regression of the [REDACTED] rSO2 data vs. the predicate system 5100C rsO2 data with the calculation of  $r^2$  assessing the linear relationship between the two continuous variables. Calculations and fitted line plots will be performed for pooled population data. Regression coefficients, slope and intercept will be reported with bootstrap 95% Confidence Limits.
- 2 Bland Altman plot (Bland and Altman, 1986), (Bland and Altman, 2007) defined limits of agreement provide the approach to agreement between different methods for measuring the same quantity. Individual subject and pooled population data will be graphed.
- 2 Random Coefficients Model; subject dependent variable added to model as random effect. This is performed on pooled data across subject study population and addresses the dependence of subject based repeated measurements. Regression coefficients, slope and intercept will be reported with bootstrap 95% Confidence Limits.
- 3 Concordance correlation coefficient (CCC) analysis (Lin, 1). This index is the correlation between the two paired measurements that fall on the 45° line through the origin.

This document is electronically controlled. Printed copies are considered uncontrolled.

Confidential MDT16010MAVJB3	[REDACTED]	[REDACTED]
---------------------------------------	------------	------------

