- 5) Subject's Skin tone will be evaluated and recorded (e.g. light, medium, and dark) will be evaluated and recorded on provided study eCRFs.
- 6) Blood pressure (BP) and Heart rate (HR) will be recorded at enrollment visit 1. BP and HR continuously will be monitored during desaturation phase.
- 7) Jugular bulb and arterial catheters will be inserted for each subject. Jugular bulb catheter will be placed under ultrasound guidance and placement will be verified with a single lateral skull x-ray. The tip of the jugular catheter should be positioned cephalad to the inferior border of the first cervical vertebrae (C1) to minimize the risk of jugular venous blood mixing with extra-cranial effluent venous drain. Side and location of the catheters will be recorded in the study provided eCRFs.
- 8) Two investigational NIRS sensors will be placed on the forehead.
- 9) Two sensors (investigational and legacy) will be placed on somatic site (e.g. calf) of the subjects.
- 10) De-identified images may be taken on the locations before and after sensor application(s).
- 11) Each subject will complete a series of Desaturation Sequence steps (#1-18) with incremental reduction/increase of SpO₂ to target ranges between 70-100%. Each subject will complete three Desaturation Sequences (████████). For more details, refer to *Section 10.5*.
- 12) The arterial (SaO₂) and venous (SjvO₂) blood draws will be repeated to target two paired samples per step. A total of █ paired arterial and venous draws (pair = 1 jugular: 1 arterial) will be collected during the study. The jugular sample will be drawn approximately over a period of █ seconds (████████). For more details, refer to *Section 10.5*.
- 13) Information will be collected throughout the study with starting Visit 1, Enrollment Phase and through Follow-up Phase. Adverse Event assessment for the purposes of this study will cease

This document is electronically controlled. Printed copies are considered uncontrolled.

Confidential MDT16010MAVJB3	████████	████	████
---------------------------------------	----------	------	------

after follow-up phone call within 48 hours after desaturation visit. All Adverse Events, regardless of relatedness or outcome, must be reported. For more details, refer to *Section 12*.

- 14) The local laboratory will be used for all laboratory assessments.
- 15) Hemoglobin electrophoresis is used to identify variant and abnormal hemoglobin.

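### The somatic regression makes no allowance for error in the legacy oximeter, so read as least squares its expected slope is below 1 even for identical devices; errors-in-variables results should stand beside it.

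*SAP*

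**What the plan says.** SAP 7.8 sets the somatic comparison out as "At the somatic site, by comparing next generation INVOS" rSO2 with the legacy device's rSO2. Under Somatic Accuracy Trending, the first item is a regression of the new device's rSO2 "vs. the predicate system 5100C" rSO2, with r², "assessing the linear relationship between the two continuous variables". The data are pooled: "Calculations and fitted line plots will be performed for pooled population data". The output is also stated: "Regression coefficients, slope and intercept will be reported with bootstrap 95% Confidence Limits".

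A random coefficients model with subject as a random effect follows, reported in the same way. Its stated purpose is that it "addresses the dependence of subject based repeated measurements". Bland-Altman plots and Lin's concordance correlation coefficient (CCC) complete the list.

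The predictor comes from a second sensor on the body. Protocol 10.1, in the notes to the Schedule of Events, says: "Two sensors (investigational and legacy) will be placed on somatic site (e.g. calf) of the subjects". SAP 5 lists "2 blood draws and monitor measurements at each oxygenation plateau" and takes the first point of each sequence as the trending baseline.

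The SAP names no regression estimator for this analysis and does not mention measurement error in the legacy device. The primary statistic in SAP 7.8 is pooled A_RMS, and Protocol 14.1 also states the somatic trending criterion in terms of A_RMS.

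**The concern.** The somatic section follows the same template as the cerebral one, but the reference is different in kind. At the cerebral site the predictor is calculated from co-oximetry of blood samples, each analysed more than once and averaged (Protocol 10.5.1). At the somatic site it is another optical device with its own noise. Least squares treats the predictor as known exactly. Noise in the predictor flattens the fitted line, and the bootstrap limits then centre on the flattened value.

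Somatic trending is part of the primary objective, and the SAP commits to reporting this slope in two models. Readers will compare it with 1. A value clearly below 1 invites the conclusion that the new device under-reports somatic change, when some or all of the shortfall may be legacy-device noise.

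**Working it through.** **What can and cannot be reproduced.** The SAP gives no expected slope, reliability or device error for this regression. Its only figure for somatic trending is 25 subjects (SAP 6). That rests on a redacted mean, SD, power and alpha for A_RMS, so it cannot be reproduced and does not bear on the slope.

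**Formula.** Take two identical devices reading the same true value T: legacy x = T + e_x and new y = T + e_y, with equal error variance and error correlation ρ. The expected least-squares slope of y on x is

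(var T + ρ·var e) / (var T + var e).

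This equals 1 only if var e = 0 or ρ = 1. The direction therefore needs no redacted number.

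**Size under assumed SDs (points of rSO2).** None of these SDs is in the documents.

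| True SD | Error SD | Slope, ρ = 0 | Slope, ρ = 0.5 |
|---|---|---|---|
| 8 | 2 | 64/68 = 0.94 | 66/68 = 0.97 |
| 5 | 2 | 25/29 = 0.86 | 27/29 = 0.93 |
| 5 | 3 | 25/34 = 0.74 | 29.5/34 = 0.87 |
| 4 | 3 | 16/25 = 0.64 | 20.5/25 = 0.82 |

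For identical devices the expected slope also equals the correlation. The extremes at ρ = 0 thus imply r² of 0.94² = 0.88 and 0.64² = 0.41.

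**Simulation in the trial's layout.** Inputs from the documents: 25 subjects (SAP 6); sequences of 8, 5 and 5 steps (Protocol 10.5.1); two readings per step (SAP 5). Assumed: between-subject SD 6, within-sequence true SD 2.67 or 4.45, error SD 1 to 3, identical devices.

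- Absolute scale: mean least-squares slope 0.98 to 0.82 (ρ = 0) and 0.99 to 0.91 (ρ = 0.5).
- Change from the first point of each sequence: 0.90 to 0.26 (ρ = 0) and 0.95 to 0.63 (ρ = 0.5). Differencing removes between-subject spread and adds baseline error to both axes.
- Deming regression with ratio 1, which is correct here: 0.999 to 1.002 (absolute) and 0.996 to 1.015 (change).

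Which scale the regression uses cannot be settled, because the trending error is defined in a SAP figure that is not shown.

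**Reverse regression.** With within-sequence SD 4.45, error SD 2 and ρ = 0, new on legacy gave 0.931 and legacy on new gave 0.928. Both fall below 1, so the shortfall is not a device difference. Inverting the second gives 1/0.928 = 1.08, and the interval 0.93 to 1.08 contains the true slope of 1.

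**Random coefficients model.** Its subject effects handle clustering, not error in x. Once subject levels are absorbed, within-subject spread drives the attenuation, so the pooled-spread figures above do not carry over to it unchanged.

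**Can the two readings per plateau supply the Deming ratio?** Only in part. The true slope is 1 throughout.

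- Purely short-term error, legacy SD 3 and new SD 1.5: least squares gave 0.83 (absolute) and 0.34 (change). Deming with the replicate-estimated ratio gave 1.00 and 1.01. A fixed ratio of 1 gave 0.93 and 0.51.
- Error that persists through a plateau, legacy SD 3 and new SD 1, with within-plateau noise of SD 1 on both: the true ratio is (1 + 1)/(9 + 1) = 0.2, but the replicates estimate 1.00. Deming then gave 0.905 and 0.634.
- When the new device carried more of the persistent error, replicate-ratio Deming erred the other way, at 1.12.

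No single ratio is safe.

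**The case against.** **Nothing readable turns on the slope.** This stands. The primary statistic is pooled A_RMS, and the slope is reported with no acceptance limit in the readable text. Attenuation makes the new device look worse, so it cannot help a poor device pass.

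**Other planned outputs already help.** A reader might infer that the planned analyses cannot separate legacy noise from under-tracking. The SAP does not support that. Bland-Altman and CCC treat the devices symmetrically, and r² is reported beside the slope. In a simulation of identical devices with error SD 2, the slope was 0.908, the correlation 0.907, and the trend of difference on mean 0.001. Someone who reads all the outputs can recognise scatter. The protection is partial, however: if the legacy device is noisier than the new one, neither check settles the question.

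**The estimator is inferred.** This also stands. Least squares is the ordinary reading of a regression with r² and fitted line plots, but the SAP does not say so. If an errors-in-variables fit is intended, it needs to be named.

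**Deming has its own weakness.** A reader might infer that one Deming slope, with its ratio taken from the two readings per plateau, should replace the planned fit. The documents do not support going that far. Both readings fall within one step of about 2 to 6 minutes (Protocol 10.5.1), so they show short-term repeatability and miss error that persists through the step. SAP 5 also does not say separately that both somatic devices are read twice. On a change scale, the common baseline correlates the errors, whereas standard Deming regression assumes they are independent. These points argue for a range of ratios beside the planned fit, not for leaving the slope uncorrected.

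**Conclusion.** The point holds as a modest one about a supportive output. If both somatic regressions are least-squares fits, their expected slope for identical devices is below 1 whenever the legacy device has error that the new device does not fully share. Neither the bootstrap limits nor the subject random effects remove this.

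The size is not known. The range 0.94 to 0.64 rests on assumed SDs and independent errors. The two sensors use the same technology on the same subject, so some shared error is plausible; at a correlation of 0.5 the shortfall is halved. A change-from-baseline analysis could show a larger shortfall.

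A reader might infer that the somatic validation result itself is biased. It is not affected by this choice: A_RMS is calculated from paired differences and does not use the regression.

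**What to change.** Keep the planned regression and plot, name the estimator, and add the following to SAP 7.8 for the somatic site:

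- The reverse regression (legacy on new), inverted to the same scale. When errors are independent, the two slopes bracket the underlying relation.
- Deming slope and intercept, with bootstrap limits from resampling subjects, over a pre-specified range of error-variance ratios. The range should include 1 and the ratio estimated from the two readings per plateau, with a note that those replicates capture short-term error only.
- A statement that a least-squares slope below 1 is not by itself evidence that the new device under-tracks.
- The scale used, absolute or change from baseline, if the figure does not already fix it.

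This needs SAP wording and standard method-comparison code, with no new data or procedures. The downsides are a little more analysis work and a Deming result that depends on the assumed ratio, which is why a range is reported.
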